10. STATISTICS

10.1. Sample Size Determination

Approximately 180 participants will be randomized 1:1 to ruxolitinib 1.5% cream BID or vehicle cream BID. The sample size calculation is based on the Fisher exact test for the primary efficacy endpoint, which is the proportion of participants with WI-NRS4 response at Week 12. The mechanism of stopping the itch-scratch cycle and reducing the pruritus are similar between PN and AD. Additionally, based on the results from a Phase 2 study in AD of nemolizumab (Silverberg et al 2020), and a Phase 2 study in PN (Galderma 2021) and a Phase 3 study in PN (Galderma 2022) of nemolizumab, the improvement in WI-NRS are not substantially different between AD and PN; therefore, the results from the 2 Phase 3 studies of ruxolitinib cream (INCB 18424-303 and -304) in the treatment of AD are used to build the assumptions of the proportion of participants with WI-NRS4 response, which are 50% for ruxolitinib 1.5% cream BID and 25% for vehicle cream BID. Using a 2-sided alpha of 0.05, the sample size based on the current assumption will have > 90% power to detect a difference between ruxolitinib cream and vehicle cream. In addition, the assumptions and powers for key secondary endpoints are provided in Table 12.

Table 12: Powering for Key Secondary Endpoints

Variables	Response Rates in Ruxolitinib 1.5% BID	Response Rates in Vehicle BID	Power: 1.5% BID vs Vehicle BID
WI-NRS4 response at Week 4	40%	15%	>90%
Overall-TS (WI-NRS4 response and IGA-CPG-S-TS) at Week 12	30%	10%	>90%
IGA-CPG-S-TS at Week 12	40%	20%	80%
WI-NRS4 response on Day 7	30%	10%	>90%

Note: Based on Fisher's exact test, 2-sided α = 0.05.

In addition to providing adequate power for efficacy variables, the sample size is determined to provide an adequate database for safety evaluations.

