10.4. Statistical Analyses

10.4.1. Primary Analysis

The primary analysis will be based on the ITT population. The baseline WI-NRS score will be determined by averaging the 7 daily NRS scores before Day 1 (Day -7 to Day -1). The by-visit WI-NRS score for postbaseline visits will be determined by averaging the 7 daily NRS scores before the visit day. If 4 or more daily scores are missing (out of the 7), the WI-NRS score at the visit will be set to missing. The proportion of participants with a WI-NRS4 response, defined as achieving a \geq 4-point improvement in WI-NRS score from baseline to Week 12, will be

summarized by treatment groups. Table 14 presents the summary of the primary endpoint analysis.

Table 14: Summary of Primary Analysis

Parameter	Definition
Treatment	Ruxolitinib 1.5% cream compared with vehicle cream
Population	ITT population
Variable	WI-NRS4 response at Week 12
Population-level summary	WI-NRS4 response rate difference with 95% CI

The primary alternative hypothesis (superiority of active ruxolitinib group 1.5% BID compared with vehicle) will be tested at a 2-sided $\alpha = 0.05$ level using a CMH test stratified by stratification factors IGA-CPG-S score (2 or \geq 3) and geographic region (North America or outside of North America). The p-value and stratum-adjusted WI-NRS4 response rate difference with 95% CI will be provided. Overall odds ratio will also be provided with 95% CI. Participants with missing Week 12 data for any reason and participants who develop AD lesions will be defined as nonresponders. No rescue therapy is allowed in this study.

Subgroup analysis by baseline characteristics such as geographic region and any underlying condition known to be associated with the clinical presentation of PN will be performed. In addition, the following sensitivity analyses may be performed, and details will be provided in the SAP.

• Longitudinal logistic regression with repeated measures:

To adjust for the dependence underlying the hierarchical multilevel data structure (visit, participant, and site), a longitudinal logistic regression with repeated measures will be applied. In the model, visits are nested within participants, which are further nested within sites.

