 - Instruction of the participant to undergo some laboratory tests at a local (nearby) hospital laboratory or facility closer to the participant's residence rather than at the investigational site. In this case, the study physician will provide the participant with the list of parameters to be checked. These tests should be performed at certified laboratories and copies of results provided to the site.

Mandatory On-Site Visits:

The visits outlined below must be performed in person in order to capture the investigator's efficacy assessments and the patient-reported outcomes, even if the date that the participant eventually comes into the clinic deviates from the visit window.

No efficacy assessments can be performed via telemedicine (video call, phone call, or photography).

The visit window deviation must be documented, and the sponsor's representative must be informed of when it is believed that the participant can come into the clinic. Further instructions will be provided if needed.

During the DBVC period, the following visits must be performed in person:

- Screening
- Day 1 (baseline)
- Week 4, 8, and 12 visits

During the OLE period, the following visits must be performed in person:

• Week 52 visit

Investigational Medicinal Product Dispensing and Distribution

In order to ensure the continuity of providing their participants' clinical supplies within the constraints imparted by the pandemic, the site staff can decide to supply study cream via shipment to participants.

If the participant cannot attend a visit at the study site, adequate supplies of study cream determined by the investigator can be shipped to the participant by the investigator or appropriately delegated staff (eg, the study pharmacy staff) using a third-party service if duly authorized by the participant.

The study site may use their own preferred courier, provided the courier adheres to certain standards (eg, use of personal protection equipment or maintenance of temperature-controlled transit environment), or one centrally contracted by the sponsor.

Clinical Trial Monitoring

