3.3. Sample Size Considerations

Approximately 180 participants will be randomized 1:1 to ruxolitinib 1.5% cream BID or vehicle cream BID. The sample size calculation is based on the Fisher exact test for the primary efficacy endpoint, which is the proportion of participants with WI-NRS4 response at Week 12. The mechanism of stopping the itch-scratch cycle and reducing the pruritus are similar between PN and AD. Additionally, based on the results from the following nemolizumab studies: a Phase 2 study in AD (Silverberg et al 2020), a Phase 2 study in PN (Galderma 2021), and a Phase 3 study in PN (Galderma 2022), the improvement in WI-NRS is not substantially different between AD and PN. Therefore, the results from 2 Phase 3 studies (INCB 18424-303 and INCB 18424-304) of ruxolitinib cream in the treatment of AD are used to build the assumptions of the proportion of participants with WI-NRS4 response, which are 50% for ruxolitinib 1.5% cream BID and 25% for vehicle cream BID. Using a 2-sided $\alpha = 0.05$, the sample size based on the current assumption will have > 90% power to detect a difference between ruxolitinib cream and vehicle cream. In addition, the assumptions and powers for key secondary endpoints are provided in Table 2.

Table 2: Powering for Key Secondary Endpoints

Variables	Response Rates in Ruxolitinib 1.5% BID	Response Rates in Vehicle BID	Power: 1.5% BID vs Vehicle BID
WI-NRS4 response at Week 4	40%	15%	> 90%
Overall-TS (WI-NRS4 response and IGA-CPG-S-TS) at Week 12	30%	10%	> 90%
IGA-CPG-S-TS at Week 12	40%	20%	80%
WI-NRS4 response on Day 7	30%	10%	> 90%

Note: Based on Fisher's exact test, 2-sided α = 0.05.

In addition to providing adequate power for efficacy variables, the sample size is determined to provide an adequate database for safety evaluations.

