7.3. Analysis of the Primary Efficacy Parameter

7.3.1. Primary Efficacy Analysis

The primary analysis will be based on the ITT Population in the DBVC period. A summary of the primary endpoint analysis is provided in Table 5.

Table 5: Summary of Primary Analysis

Parameter	Definition	
Treatment	Ruxolitinib 1.5% cream compared with vehicle cream	
Population	ITT Population	
Variable	WI-NRS4 response at Week 12	
Population-level summary	WI-NRS4 response rate difference with 95% CI	

Note: Participants with missing Week 12 data for any reason, including treatment discontinuation (due to development of AD lesions or any other cause), will be defined as nonresponders. No rescue therapy is allowed in this study.

The WI-NRS score at each postbaseline visit (ie, the by-visit WI-NRS score), will be determined by averaging the 7 daily NRS scores before the visit day. If 4 or more daily scores are missing (out of the 7), the WI-NRS score at the visit will be set to missing. Missing WI-NRS scores at each postbaseline visit will be imputed as nonresponders for the primary analysis. The baseline for the by-visit WI-NRS score will be determined by averaging the 7 daily NRS scores before Day 1 (ie, Day -7 to Day -1). The proportion of participants with a WI-NRS4 response, defined as achieving a \geq 4-point improvement in the by-visit WI-NRS score from baseline, will be summarized by treatment group and visit.

The primary hypothesis specified in Section 7.1 will be tested at a 2-sided $\alpha = 0.05$ level using a CMH test stratified by IGA-CPG-S score (2 or \geq 3) and geographic region (North America or outside of North America). The p-value and stratum-adjusted WI-NRS4 response rate difference with the 95% CI will be provided. An overall odds ratio will also be provided with the 95% CI.

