7.4. Analysis of the Key Secondary Efficacy Parameters

All key secondary efficacy analyses will be conducted on the ITT Population in the DBVC period.

If the primary objective is achieved, the statistical hypotheses for the following key secondary endpoints will be tested in a fixed sequence at a 2-sided $\alpha = 0.05$ level in the following order:

- 1. WI-NRS4 response at Week 4
- 2. Overall-TS at Week 12
- 3. IGA-CPG-S-TS at Week 12
- 4. WI-NRS4 response on Day 7

The statistical comparisons for the key secondary endpoints, WI-NRS4 at Week 4, Overall-TS at Week 12, and IGA-CPG-S-TS at Week 12, will be analyzed using the similar method as specified in the primary analysis. Missing values at each visit will be imputed as nonresponders.

For the composite endpoint Overall-TS, defined as achieving both a WI-NRS4 response and an IGA-CPG-S-TS, the by-visit WI-NRS score (as defined in Section 7.3.1) will be used to derive the Overall-TS response.

For the WI-NRS4 response on Day 7, daily WI-NRS scores will be used for the analysis. Baseline will be defined as the last available daily WI-NRS score during the last week prior to Day 1 (ie, Days −7 to −1). Missing daily WI-NRS scores from Day 1 to Day 7 will be imputed using the similar multiple imputation method as outlined in the sensitivity analysis for the primary endpoint. Specifically, a regression model, including treatment group, stratification factors, baseline daily WI-NRS score, and daily WI-NRS scores from Day 1 to Day 7, will be specified for the fully conditional specification method. For each imputed dataset, the proportion of participant with an WI-NRS4 response on Day 7, defined as a ≥ 4-point improvement (reduction) in daily WI-NRS score from baseline to Day 7, will be analyzed using the CMH test as specified for the primary analysis. Then the results will be combined for inference using Rubin's rule.

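### By-visit itch scores are tied to the clinic visit day with no target day or analysis window, so a missed or very late visit can discard or misplace diary data that were observed

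*SAP*

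**What the plan says.** Protocol 10.4.1 defines the score this way: "The by-visit WI-NRS score for postbaseline visits will be determined by averaging the 7 daily NRS scores before the visit day". SAP 7.3.1 repeats the rule, saying that the by-visit score "will be determined by averaging the 7 daily NRS scores before the visit day"; SAP 7.2.1 has it too, and SAP 7.4 applies the by-visit method to the Week 4 endpoint and to the itch part of Overall-TS. At least 4 of the 7 daily scores must be present. A missing score is nonresponse for the primary endpoint (SAP 7.3.1). For the visit-based key secondary endpoints, SAP 7.4 states: "Missing values at each visit will be imputed as nonresponders".

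The diary does not depend on attendance. Protocol 8.2.1 and SAP 7.2.1 have it completed each evening from screening onward.

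Protocol Table 3 gives the Week 2, 4, 8 and 12 visits a ±3-day window. Under pandemic conditions, Appendix B requires the Week 4, 8 and 12 visits in person "even if the date that the participant eventually comes into the clinic deviates from the visit window", and sets no upper limit on the delay. SAP 4.1 defines Day 1, study day, baseline and partial dates. It gives no target day, no analysis window and no rule for a missed or out-of-window visit. Among the itch endpoints in the testing sequence, only the Day 7 response is scored by study day (SAP 7.4).

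**The concern.** The anchor for a home diary score is an event that has nothing to do with whether the diary was kept. Two consequences follow if the text is applied as written.

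- **Missed visit.** Without a visit there is no visit day, so there are no 7 days before it. The score is missing and the participant is a nonresponder, even with all 7 entries recorded around the intended date. The clearest case is Week 4 in a participant who stays on treatment.
- **Very late visit.** The week before the actual visit is labelled Week 4 or Week 12, although diary entries for the intended week exist.

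The endpoints affected are the primary and the first key secondary, and the latter gates the rest of the fixed sequence. The multiple imputation and tipping point analyses (SAP 7.3.3.3 and 7.3.3.4) cover only the primary endpoint and would treat the unused diary week as missing. The per-protocol analysis drops participants without a Week 12 score (SAP 5.3.2). None of these restores the observed data. Two programmers could also derive different endpoints from the same data, because nothing says what to do when the visit date is absent.

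**Working it through.** **Inputs.** SAP 3.3: "Approximately 180 participants will be randomized 1:1 to ruxolitinib 1.5% cream BID or vehicle cream BID", so 90 per arm. SAP 3.3 also says "The sample size calculation is based on the Fisher exact test for the primary efficacy endpoint", with rates "which are 50% for ruxolitinib 1.5% cream BID and 25% for vehicle cream BID" at Week 12. SAP Table 2 gives 40% and 15% at Week 4. The plan's claim (Protocol 10.1) is: "Using a 2-sided alpha of 0.05, the sample size based on the current assumption will have > 90% power". Table 2 also gives more than 90% for Week 4.

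**Step 1: reproduce the stated power.** Power = Σₓ Σᵧ Bin(x; 90, p₁) · Bin(y; 90, p₂) · 1{two-sided Fisher p(x, y) ≤ 0.05}, summed over all pairs.

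- Week 12, 0.50 vs 0.25: 92.3%.
- Week 4, 0.40 vs 0.15: 95.9%.

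Both agree with the plan.

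**Step 2: effect of lost responders.** Let m be the share of would-be responders, equal in both arms, who are scored as nonresponders because the visit was missed although the diary was complete. Each rate becomes p(1 − m). No value of m can be taken from the documents, so a range is shown.

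| m | Week 12 rates | Week 12 power | Week 4 rates | Week 4 power |
|---|---|---|---|---|
| 0 | 50% vs 25% | 92.3% | 40% vs 15% | 95.9% |
| 1% | 49.5% vs 24.75% | 91.8% | 39.6% vs 14.85% | 95.6% |
| 3% | 48.5% vs 24.25% | 90.9% | 38.8% vs 14.55% | 95.1% |
| 5% | 47.5% vs 23.75% | 89.8% | 38% vs 14.25% | 94.5% |
| 10% | 45% vs 22.5% | 86.9% | 36% vs 13.5% | 92.7% |

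For scale, m = 5% at Week 12 means 90 × 0.50 × 0.05 = 2.25 expected responders lost on ruxolitinib and 90 × 0.25 × 0.05 = 1.125 on vehicle. The Week 12 difference shrinks from 25 points to 25 × 0.95 = 23.75.

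**Step 3: timing shift.** A visit d days off target shares max(0, 7 − d) scored days with the target week.

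- d = 3: 4 of 7 days shared.
- d = 5: 2 of 7.
- d = 7 or more: none.

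**Step 4: target days.** SAP 4.1.2 counts the first application as Day 1. If Week k is taken as Day 7k + 1, Week 4 is Day 29 and Week 12 is Day 85, and the 7 preceding days are Days 22–28 and 78–84. The documents do not define these days; they are an assumption.

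**The case against.** The strongest reply is that neither document says a missed visit makes a complete diary missing. The only stated trigger is too few diary entries. Table 3 labels its columns by nominal visit day, so a programmer might use the scheduled day. This stands in part: nonresponse after a missed visit follows from the text but is not a written rule. Nothing in the SAP prescribes the scheduled day either.

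Conduct rules also shrink the problem. Sites must reschedule a missed visit promptly (Protocol 7.3) and contact participants a week before each visit about diary completion (8.2.1). At Week 12, participants who never attend will mostly have discontinued. For them nonresponse is the planned handling, and the diary would usually have stopped as well. All of this stands, and it makes Week 4 the more plausible case.

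Four stronger readings are tempting but not supported.

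- **Attendance at Week 4 is optional.** Appendix B lists it among the visits that must be in person, even if late.
- **Late visits are expected.** Appendix B is a contingency; it permits them.
- **A late Week 12 visit brings in open-label data.** The notes to Table 3 require all Week 12 assessments before entry to the extension, so the issue is timing only.
- **The comparison is biased between arms.** At Week 12, losing 10% of would-be responders would give 76.8% power if the loss were in the ruxolitinib arm only and 96.5% if in the vehicle arm only. Nothing in the documents suggests either pattern.

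**Conclusion.** The gap is real: the score is anchored to attendance, and there is no target day, window or fallback. Applied literally, the rule can discard an observed diary week after a missed visit and score a different week after a visit 7 or more days late. Inside the ±3-day window the effect is minor.

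The likely size is small. A reader might infer that the trial falls short of its stated power. The documents do not show that. Week 12 power drops just below 90% only at about 5% of would-be responders lost in both arms (89.8%; it is still 90.9% at 3%). Week 4 power stays above 90% throughout the range shown.

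These figures rest on an assumed m, on equal loss by arm, and on the design rates applying before any such loss. The plan does not say whether those rates already allow for missing scores. The case for a change is that observed data should be used and the derivation fixed in advance, at almost no cost.

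**What to change.** In SAP 7.2.1, 7.3.1 and 7.4, with a matching definition in 4.1:

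1. Define a target study day for Week 4 and Week 12, for example Days 29 and 85, for the sponsor to confirm.
2. Keep the 7 days before the visit when it falls within ±3 days of target.
3. When the visit is missed or outside that window, use the 7 diary days before the target day (Days 22–28 or 78–84 on the example), still requiring at least 4 of 7 entries.
4. Leave unchanged the existing nonresponder handling for treatment discontinuation and development of AD lesions, and state that it takes precedence over the fallback. Otherwise a participant who stopped for AD lesions but has diary entries in the fallback window could become a responder.
5. In all other cases, impute nonresponse only if the fallback window also lacks enough entries.

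The cost is SAP wording and programming, with no new data. Because the SAP covers both INCB 18424-319 and -320, one edit serves both studies. There is a small downside: for off-window visits, the itch week and the clinic IGA used in Overall-TS come from different days. A missed visit still loses the IGA part of that endpoint, which the fallback cannot restore.

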7.3.2. Subgroup Analyses for Primary Endpoint

Subgroups will be formed based on the following participant characteristics and baseline variables for those participants whose data are available:

- Baseline IGA-CPG-S score: 2 or ≥ 3
- Geographic region: North America or outside of North America
- Sex: female or male
- Race: White/Caucasian, Black or African American, or Asian and Others
- Age group: 18 to < 65 years or \ge 65 years
- Ethnicity: Hispanic or Latino or Not Hispanic or Latino and Others

The primary endpoint will be summarized and analyzed using descriptive statistics based on the ITT Population for the aforementioned subgroups in the DBVC period.

7.3.3. Supportive and Sensitivity Analyses for the Primary Endpoint

7.3.3.1. Per Protocol Population Analysis

Supportive analysis will be performed for the PP Population (defined in Section 5.3.2) using the same method as the primary analysis.

7.3.3.2. Longitudinal Logistic Regression With Repeated Measures

To adjust for the dependence underlying the hierarchical multilevel data structure (ie, visit, participant, and site), a longitudinal logistic regression with repeated measures will be applied. In the model, visits are nested within participants, which are further nested within sites.

The primary endpoint binary response of the participant at each of the postbaseline scheduled visits up to Week 12 will be included as the dependent variable. Treatment (ruxolitinib 1.5% cream BID and vehicle cream BID), randomization stratification factors, visit, and treatment by visit interaction will be included as fixed effects. Site-level intercept and participant nested in site-level intercept will be included as random effects. The within-participant and within-site errors will be modeled by an unstructured variance-covariance matrix. The Kenward-Roger approximation will be used to estimate denominator degrees of freedom for this model.

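### The longitudinal logistic sensitivity model combines a participant random intercept with an unstructured within-participant error matrix, so it is over-parameterised and unlikely to fit stably as written

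*SAP*

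**What the plan says.** SAP 7.3.3.2 describes a longitudinal logistic regression intended to allow for dependence among visits, participants and sites. The outcome is binary: whether the participant is a WI-NRS4 responder, taken at every scheduled visit after baseline through Week 12. The fixed effects are treatment, the stratification factors, visit and treatment by visit. Two sentences then set the covariance. One gives the random effects: "Site-level intercept and participant nested in site-level intercept will be included as random effects". The other, placed after it, deals with the errors and asks for a general matrix at both levels: "The within-participant and within-site errors will be modeled by an unstructured variance-covariance matrix".

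The section closes by fixing the degrees-of-freedom method: "The Kenward-Roger approximation will be used to estimate denominator degrees of freedom for this model". Protocol 10.4.1 carries the same specification.

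Neither document says that the unstructured matrix replaces the participant intercept. Neither names an estimation method, a simpler covariance structure to fall back on, or a rule for non-convergence. The Protocol makes the analysis optional ("the following sensitivity analyses may be performed, and details will be provided in the SAP"). The SAP commits to it, although no table title in SAP Appendix A identifies it.

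**The concern.** A random intercept for participant adds the same covariance to every pair of that participant's visits, and the same amount to every variance. An unstructured matrix over those visits can already reproduce any such pattern. Asking for both gives the model two places to put one quantity.

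The within-site part of the sentence raises a separate difficulty. An unstructured matrix needs a fixed set of positions, and sites hold different numbers of participants.

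At stake is one of the three sensitivity analyses of the primary endpoint that SAP 7.3.3 lists beside the per-protocol analysis. If the model fails and no fallback is written down, it is either dropped or simplified ad hoc. Under SAP Section 10 the sponsor is unblinded once the primary database is locked, so a simplification made at that stage would be made with treatment codes available. SAP Section 1 applies the same plan to studies 319 and 320, so the two could end up with different improvised models.

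**Working it through.** **Inputs from the documents.** The post-baseline visits up to Week 12 are Weeks 2, 4, 8 and 12 (Protocol Table 3), so T = 4. On sample size: "Approximately 180 participants will be randomized 1:1 to ruxolitinib 1.5% cream BID or vehicle cream BID", taken as 90 per arm. Week 12 response rates: "which are 50% for ruxolitinib 1.5% cream BID and 25% for vehicle cream BID". Week 4 rates are 40% and 15% (SAP Table 2).

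**Inputs assumed.** The documents give no Week 2 or Week 8 rates. Two sets of paths were used (active; vehicle, at Weeks 2/4/8/12):

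- Path A: 25/40/47/50%; 8/15/21/25%.
- Path B: 33/40/45/50%; 12/15/20/25%.

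The working matrix R has unit variances and a common correlation of 0 or 0.3.

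**The plan's own figure.** No stated figure depends on this model. The nearest is primary-endpoint power. Exact enumeration of the Fisher test at 50% vs 25%, 90 per arm, two-sided 0.05, gives 92.3%, in line with the stated value above 90%.

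**Step 1: linear working scale.** Write V = σ²J + R, with J the 4×4 matrix of ones and R unstructured.

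- R has 4×5/2 = 10 free elements. With σ² there are 11 parameters.
- V has only 10 distinct elements, and the derivative of V with respect to the 11 parameters has rank 10.
- Adding the site intercept gives 12 parameters and rank 11. The site term is identified because it also links different participants; the participant intercept is the redundant one.

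Example: let σ² = 1.5 and let R have variances 1 and covariances 0.3. V then has variances 2.5 and covariances 1.8. Setting σ² = 0 with R variances 2.5 and covariances 1.8 gives the same V. So does σ² = 1.79 with R variances 0.71 and covariances 0.01. R is positive definite in each case, so no data could choose between them on this scale.

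**Step 2: logistic pseudo-likelihood scale.** Here V = σ²J + A^(−1/2) R A^(−1/2), with A = diag{μ(1−μ)}. The information for parameters k and l is the sum over participants of ½ tr(V⁻¹ ∂V_k V⁻¹ ∂V_l). If μ is the same at all visits in both arms, this matrix is singular. With unequal rates it can be inverted, but only just. At a true σ² of 1.0:

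| Path | Working correlation | SE of σ² | SE if R were known | Ratio |
|---|---|---|---|---|
| A | 0 | 0.92 | 0.25 | 3.7 |
| A | 0.3 | 1.35 | 0.37 | 3.7 |
| B | 0 | 0.95 | 0.24 | 3.9 |
| B | 0.3 | 1.39 | 0.36 | 3.8 |

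The standard error is about as large as the variance being estimated, or larger. A fairer comparator than a known R is a scalar residual, which could actually be fitted: at a true value of 1.5, the SE was 1.14 for the combined model against 0.31.

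**Step 3: trial fits.** Data were simulated for 90 per arm on Path B and fitted by REML pseudo-likelihood, 25 data sets per scenario, with true intercept variances of 2 and 6.

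| Model | Converged, σ² = 2 | Converged, σ² = 6 |
|---|---|---|
| Participant intercept, scalar residual | 25/25 | 25/25 |
| Unstructured R, no participant intercept | 25/25 | 25/25 |
| Both, as written | 0/25 | 1/25 |

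The failures were divergences, with a large intercept variance and R close to singular. The simulation had no site effect, strata or missing data, and did not use the sponsor's software.

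**Step 4: within-site matrix.** A site with m participants has 4m observations and needs 4m(4m+1)/2 elements. For m = 5 that is 20×21/2 = 210; for m = 10 it is 40×41/2 = 820. The dimension changes from site to site.

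**The case against.** The strongest reply is that the sentence is ambiguous rather than wrong. It names the same two levels, participant and site, that have just received intercepts. It could therefore be giving the covariance type of those two effects. An unstructured matrix for a single intercept is 1×1, and the model reduces to two random intercepts, which fits without difficulty. This reading also gives the within-site phrase a meaning. It is possible but strained: the text says errors, in a separate sentence after the random effects, and on this reading the sentence would add nothing.

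A second reply is that the participant variance is a nuisance parameter. On the linear scale V is identified and generalised least squares uses only V, so the treatment estimate would survive. This is fair as far as it goes, and no check here measured the Week 12 treatment effect or its standard error. It does not make the logistic fit converge. In a subject-specific logistic model σ² also sets the scale of the odds ratio, by the usual approximation a factor of √(1 + 0.346σ²) on the log scale. That factor is 1.16 at σ² = 1 and 1.30 at σ² = 2.

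A third reply stands: the numerical evidence depends on assumed Week 2 and Week 8 rates and on a small simulation. The rank result in Step 1 does not.

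A fourth also stands in part: nothing prevents the sponsor from trying the model on blinded data before lock, so a choice made after unblinding is a risk and not a certainty.

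**Conclusion.** The specification is over-parameterised and should be corrected. The redundancy is exact on the linear working scale (11 parameters, rank 10) and needs no assumption. In a logistic pseudo-likelihood fit it becomes weak identification, with an SE of about 0.9 to 1.4 for a participant variance of 1.0 under the assumed rates and working correlations. A true-likelihood logistic mixed model has no free residual matrix, so there the sentence could not be implemented.

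Three stronger readings are not supported:

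- **That the two terms can never be separated.** For binary data they are formally distinguishable through the mean-variance weights; the accurate statement is that a stable fit is unlikely.
- **That a missing-data check would be lost.** SAP 7.3.3.2 gives its purpose as hierarchical dependence. Missing data are handled by nonresponder imputation in the primary analysis (7.3.1), multiple imputation (7.3.3.3) and the tipping point analysis (7.3.3.4).
- **That the primary result is at risk.** The stratified CMH test, the fixed testing sequence and the termination rule in SAP Section 10 do not use this model.

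**What to change.** Amend SAP 7.3.3.2 before unblinding:

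1. Keep the site random intercept, which is identifiable and serves the section's stated aim.
2. Keep one source of within-participant correlation: either an unstructured R-side visit covariance by participant with no participant intercept, or a participant-within-site intercept with no unstructured residual matrix.
3. Remove within-site errors from the unstructured term.
4. Name the estimation method, and confirm that it supports the Kenward-Roger adjustment already specified.
5. Prespecify an ordered fallback for non-convergence, for example compound symmetry in place of the unstructured matrix, then dropping the site effect.

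Protocol 10.4.1 defers the details to the SAP, so the departure from its wording can be recorded in SAP 11.1. The cost is SAP wording only; no data collection, sample size or primary analysis changes. One correction covers both studies under this SAP.
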